Protocol Title:

Comparison of Timing of Initiation on the Efficacy of Gabapentin in Treating
Neuropathic Pain in Spinal Cord Injury (SCI).

2/4/20

ClinicalTrials.gov Identifier: NCT04256603

Introduction:

Neuropathic pain is a common complaint in those with spinal cord injury (SCI) that has a significant negative effect on quality of life. This makes the treatment of neuropathic pain a priority in the SCI population. Efficacy of various treatments, however, remains controversial. There is evidence to support that gabapentin and pregabalin have some benefit in reducing neuropathic pain (1). Other positive effects of gabapentin on those with SCI have also been demonstrated. However, there has not been a study on the influence of timing of initiation of gabapentin on the efficacy of using it to treat neuropathic pain in the SCI population. Such a finding could change the standard of care in treatment of acute SCI.

The pooled prevalence of neuropathic pain post spinal cord injury is 53% (2). Not only common, neuropathic pain is pervasive, affecting aspects of patients' lives including sleep, physical function, and mood that in turn impact their activities—work and recreational alike (3). Thus, neuropathic pain management contributes to quality of life for a majority of people with SCI.

Although a high priority, the treatment of neuropathic pain in SCI remains notoriously difficult (4). Treatment options may be divided into pharmacologic and non-pharmacologic. Pharmacologic agents studied include amitriptyline, gabapentin, pregabalin, opiates, lidocaine, ketamine, valproate, lamotrigine, levetiracetam and carbamazepine; the most studied of which are amitriptyline, gabapentin, and pregabalin (5).

Gabapentin's potential is not limited to neuropathic pain management, making it a particularly compelling treatment option in the population with acute SCI. Gabapentin leads to improvement in total motor scores (6-9), reduced spasticity, reduced autonomic dysreflexia, and improved mood (8, 9). Animal models suggest it may be neuroprotective in the acute phase of injury (10). In those who undergo spine surgery, regardless of presence of SCI, gabapentin given perioperatively leads to reduced opiate use and decreased pain in post-operative period (11). Additionally, when compared to narcotic alternatives, gabapentin has minimal side effects.

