Neuropathic pain in SCI is common, impactful, and difficult to treat. Gabapentin is effective in the management of symptoms and concerns related to SCI including motor recovery, spasticity, and mood among others. This makes gabapentin an important pharmacologic intervention, which compels providers to define treatment guidelines related to its use. One aspect of which should relate to the timing of initiation of therapy. The goal of this study is to determine whether early initiation of treatment with gabapentin will decrease average pain scores and opiate use when compared to late initiation of treatment with gabapentin in the population with acute SCI. Gabapentin, although used commonly, is not started in all patients with acute SCI but is often started at the onset of neuropathic pain. If gabapentin is found to be more effective when initiated early, it would be reasonable to start gabapentin immediately following acute SCI in all patients in whom it is not otherwise contraindicated.

1. Objectives

- Primary

- To determine if the time from injury influences the prevalence of neuropathic pain in acute SCI
- To determine if the use of gabapentin in the early acute period influences the prevalence of neuropathic pain in patients with acute SCI
- To compare the efficacy of acute versus subacute initiation of gabapentin in treating neuropathic pain in SCI

- Secondary

- To compare the overall pain scores
- To determine the prevalence of neuropathic pain in those with SCI at admission and discharge to the inpatient rehabilitation hospital
- To compare the use of opiates
- To compare the average daily change in Functional Independence Measure (FIM)
- To compare the change in total motor score on the ASIA impairment scale
- To identify side effects of treatment with gabapentin and their frequency

2. Endpoints

Primary

- Presence of neuropathic pain at time of enrollment and again around time of discharge (Douleur Neuropathique 4, DN4)
- Neuropathic pain level (Neuropathic Pain Scale, NPS) at time of enrollment and again around time of discharge

Secondary

- Average pain level recorded in nursing flowsheet (Numeric Pain Rating Scale, NPRS)
- Weekly total use of opiates (total morphine milligram equivalents, MME)
- Change in FIM during rehabilitation
- Change in total motor score on the ASIA impairment scale during entire rehabilitation course

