- Side effects attributed directly to gabapentin in physician documentation and whether or not gabapentin was stopped due to these side effects

3. Design

- Prospective, observational, cohort, single center study
- The study will enroll subjects with acute spinal cord injury who are admitted to acute inpatient rehabilitation at MetroHealth Rehabilitation Institute (MRI).

- After enrollment, subjects will be followed through the end of their acute rehabilitation stay including any interruption in rehabilitation for which they require ED evaluation and/or acute hospital readmission so long as they return to MRI.
- Around the time of enrollment, subjects will be asked to complete the DN4 questionnaire and the NPS.
- Around the time of discharge, subjects will be asked to complete a second DN4 questionnaire and the NPS.
- The remainder of the data collection will be through review of the patient's electronic medical record (EMR).
- Patients will be divided into those who first received gabapentin during their acute inpatient hospitalization, prior to admission to acute rehabilitation, and those who did not. Additionally, the timing of gabapentin initiation will also be recorded.

4. Subject selection

- Study population

Subjects are patients who suffered acute spinal cord injury for which they are admitted to acute inpatient rehabilitation at MRI.
- Inclusion criteria

Subjects who meet all the following criteria may be given consideration for inclusion in this clinical investigation, provided no exclusion criterion is met

 1. Clinical diagnosis of acute spinal cord injury
 2. Admission to MRI for acute inpatient rehabilitation
- Exclusion criteria

Subjects who meet one or more of the following criteria will be excluded from this clinical study.

 1. Unable to communicate verbally or by writing, unable to follow basic instructions, or unable to answer questions regarding their symptoms

5. Subject Accountability

- Point of enrollment

The point of enrollment is the time at which time a subject signs and dates the valid, IRB approved informed consent form. No study-related procedure or assessments can take place until the informed consent form is signed.
- Withdrawal

All subjects enrolled to the study (including withdrawal or lost to follow-up) shall be accounted for and documented.

Reasons for withdrawal include:

 1. Physician discretion
 2. Subject choice
 3. Lost to follow up
 4. Death

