Subjects may withdraw from the study at any time, with or without reason without prejudice to further treatment.

6. Study methods

- Pre-screening

To determine eligibility for enrollment into the study, the inclusion and exclusion criteria must be assessed.

- Informed consent

After a patient has been identified as a potential candidate, based on meeting all inclusion and no exclusion criteria, written Informed Consent must be obtained by asking patients to read and review the valid IRB-approved Informed Consent. The informed consent process will abide by the MetroHealth Medical Center IRB process.

- Initial Visit

The initial visit will occur at or within 7 days of the time of enrollment and admission to rehabilitation

- o Visit Type: Visit to patient while they are admitted to hospital
 - Admission DN4 and NPS

- Final Visit

The final visit will occur at or within 7 days of the time of discharge from MRI

- o Visit Type: Visit to patient while they are admitted to hospital
 - Discharge DN4 and NPS

- Additional data collection: As outlined in Figure 2

The data collection will be completed via review of the EMR of each subject, and will include the following:

- o Demographics
 - Age
 - Sex
 - Race
 - History of drug use
 - History of smoking
- o Home pain medications prior to SCI injury
- o Date of injury
- o ASIA impairment scores (AIS; 1st documented AIS, rehabilitation admission AIS, and rehabilitation discharge AIS)
- o Operative vs nonoperative management of SCI
- o Length of stay in rehabilitation
- o Rehabilitation admission and discharge FIM scores
- o Rehabilitation admission and discharge total motor scores (TMS) as recorded on AIS
- o Pain scores (NPRS)
 - Average score per week from injury as documented in EMR
- o Opiate use
 - Total weekly MME per week from injury

- Side effects
 - Record side effects attributed to gabapentin by treating physician
 - Record if therapy was stopped and why (ineffective, no longer required, adverse reaction)

7. Statistical Analysis Plan

Subject demographics will be summarized by typical descriptive statistics to compare means or medians and measures of variability

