The relationship between the presence of neuropathic pain and: 1) the time from injury; 2) the timing of gabapentin initiation will be evaluated by building logistic regression models with dichotomous neuropathic pain (measured by DN4) as the dependent variable and time as the independent variable. Potential confounding variables will be added to the model if independently associated with the outcome of interest or based on theoretical grounds.

The efficacy of gabapentin by timing of initiation will be analyzed with a regression model with change in pain on the Neuropathic Pain Scale from admission to discharge with timing of gabapentin initiation as the independent variable. Potential confounding variables will be added to the model if independently associated with the outcome of interest or based on theoretical grounds.

8. Data analysis

- All enrolled subjects will be eligible for evaluation.

9. Data Safety/ Monitoring

The PI and co-investigators will monitor the progress of the research study, including assessments of data quality, participant recruitment, accrual and retention, subject's confidentiality, any adverse event(s), and external factors or relevant information that might have an impact on the safety or ethics of the study.

After recruitment, data analysis will occur and any changes to the risk/benefit ratio to study participation will be identified and reported to the IRB. In addition, the PI and co-investigators will meet on an annual basis and reports of the meeting will be submitted to the IRB.

If an adverse event occurs, it will be reported immediately to the MetroHealth Institutional Review Board (IRB). If an unexpected adverse event occurs, the investigators will assess the risk/benefit ratio of the study and submit any modifications deemed necessary to the IRB for approval. At the time of the IRB renewal, the PI will

submit information about the frequency of the monitoring, the dates that the monthly meeting took place, a summary of the cumulative adverse events, external factors or relevant information that might have an impact on the safety or the ethics of the study, and final conclusions regarding changes to the anticipated risk/benefit ratio to study participation and final recommendation related to the continuation, changing, or termination of the study.

10. Study Assessments

1. Assessment of presence of neuropathic pain (DN4) at time of admission and discharge

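### The gabapentin-timing DN4 model is at risk of confounding by indication: neuropathic pain before an acute-hospital start is neither listed for collection nor required as an adjustment, and the DN4 occasion is not named

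*Combined protocol and SAP*

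**What the plan says.** The second primary objective (Section 1) is "To determine if the use of gabapentin in the early acute period influences the prevalence of neuropathic pain in patients with acute SCI". The design (Section 3) is a "Prospective, observational, cohort, single center study", so the study does not assign when gabapentin starts. Section 3 divides patients into "those who first received gabapentin during their acute inpatient hospitalization, prior to admission to acute rehabilitation, and those who did not", and adds that the timing of the start will be recorded.

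The analysis for this objective is in Section 7: "the timing of gabapentin initiation will be evaluated by building logistic regression models with dichotomous neuropathic pain (measured by DN4) as the dependent variable", with time as the predictor. Confounders may be added if they are associated with the outcome or on theoretical reasoning. None is named.

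The Introduction describes usual practice: gabapentin "is not started in all patients with acute SCI but is often started at the onset of neuropathic pain". It also describes another route to an early start, noting that "gabapentin given perioperatively leads to reduced opiate use and decreased pain in post-operative period".

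The DN4 endpoint in Section 2 is "Presence of neuropathic pain at time of enrollment and again around time of discharge". Under Section 6 the initial visit falls within 7 days of enrollment and rehabilitation admission. The EMR review in Section 6 is introduced by "Additional data collection: As outlined in Figure 2"; that figure is not shown. The readable list has weekly NPRS and weekly opiate MME from injury, and the reason gabapentin was stopped. It has no neuropathic pain status, or onset date, before rehabilitation.

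**The concern.** If neuropathic pain prompts the prescription, patients started in the acute hospital will include more people who already had the outcome condition. A regression of DN4 on timing then mixes the effect of the drug with the reason it was given. Admission DN4 can serve as a pre-start value for patients who begin gabapentin after the initial visit. It cannot do so for acute-hospital starters, because by then they have been treated. They are the group the second objective concerns.

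NPRS and MME do not separate neuropathic pain from surgical or other pain, so they are at best partial proxies. The confounder clause would let the analyst include earlier neuropathic pain, but does not oblige it and cannot deliver it unless the variable is abstracted.

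The unnamed DN4 occasion adds to this. Admission DN4 and discharge DN4 answer different questions, and the NPS model in the same section does state admission to discharge. There is also an ambiguity about never-starters: Section 3 places them in the comparison group, but a model with start time as predictor gives them no value.

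The objective asks about influence, which is a causal question. The Introduction says a favourable answer would support starting gabapentin straight after injury in everyone without a contraindication. A real benefit that is hidden or reversed, or a spurious one, would matter.

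**Working it through.** The plan gives no sample size, significance level, power or effect size, so there is no figure of its own to reproduce. The calculation below illustrates the Section 3 two-group comparison. It does not quantify the Section 7 model with time as predictor.

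**Inputs.** *p* = 0.53 have neuropathic pain before rehabilitation admission (the Introduction's pooled prevalence, not this cohort's). All else is assumed: *k* = 0.80 of those still have it at discharge; *n* = 0.30 of the others have it at discharge; *a* and *b* are the chances of an acute-hospital start with and without earlier pain.

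**Formulas.** Early starters with and without earlier pain: e1 = p·a, e0 = (1−p)·b. Not-early: l1 = p(1−a), l0 = (1−p)(1−b). Discharge DN4-positive with no drug effect: early (e1·k + e0·n)/(e1 + e0); not-early (l1·k + l0·n)/(l1 + l0).

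**One case in full** (a = 0.40, b = 0.20): e1 = 0.212, e0 = 0.094, l1 = 0.318, l0 = 0.376. Early: (0.212×0.8 + 0.094×0.3)/0.306 = 0.646. Not-early: (0.318×0.8 + 0.376×0.3)/0.694 = 0.529. Odds ratio (0.646/0.354)/(0.529/0.471) = 1.63.

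**True benefit.** Apply an odds ratio of 0.5 to *k* and *n* in early starters: 0.80 becomes 0.667 and 0.30 becomes 0.176.

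| a / b | Early v not-early, no effect | OR, no effect | OR when true OR is 0.5 |
|---|---|---|---|
| 45% / 40% | 0.580 v 0.554 | 1.11 | 0.66 |
| 50% / 40% | 0.592 v 0.542 | 1.23 | 0.73 |
| 40% / 20% | 0.646 v 0.529 | 1.63 | 0.95 |
| 50% / 20% | 0.669 v 0.507 | 1.97 | 1.14 |
| 60% / 15% | 0.709 v 0.473 | 2.71 | 1.52 |

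Varying *p* (0.30, 0.53, 0.65) and *k*/*n* (80/30, 70/30, 90/20%) over the same five start patterns, 45 sets in all, gives no-effect odds ratios of 1.07 to 4.29.

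**Other start patterns, base inputs, no effect.** 40%/40%: 1.00. 35%/40%: 0.90. 30%/40%: 0.80. With 40%/40% and a true odds ratio of 0.5, the comparison gives 0.60; that gap from 0.5 comes from collapsing the two pain strata, not from confounding.

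**If never-starters were dropped** (the plan does not say so), let *c* and *d* be the chances of a rehabilitation start with and without pain. Late-starter risk is (l1·c·k + l0·n·c)/(l1·c + l0·[n·c + (1−n)·d]). Over five assumed *c*/*d* pairs (70/10, 50/10, 80/5, 70/30, 60/40%) the no-effect odds ratio runs from 0.31 to 1.93 at base *p*, *k*, *n*.

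**Check of the remedy.** A day-by-day model of pain onset and gabapentin start was used, with admission on day 21, discharge on day 60, a daily onset hazard of 0.0353 and then 0.0120, and start hazards set to give the five *a*/*b* pairs (all assumed). With no drug effect:

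- Pain status and exposure both read at one common day (7, 14 or 21): odds ratio 1.00, whether by adjustment or by restriction to pain-free patients.
- A starter's own start date set against a fixed day for the others: 0.93 to 1.66 by adjustment, 1.05 to 1.26 by restriction.

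**The case against.** A reader might infer that the model is confounded as a matter of fact, that prior neuropathic pain is not collected, and that the bias must run against early gabapentin. The documents support none of these.

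- *Collection.* Figure 2 cannot be read and the Section 6 list is not exhaustive. It also omits the gabapentin start date, which Section 3 says will be recorded. Absence from the list is therefore weak evidence of absence from the plan.
- *Adjustment.* The confounder clause covers earlier pain on theoretical reasoning, and operative management is collected. What stands is that nothing is required, and the readable list has no specific variable to use.
- *Direction.* Perioperative use is a second route to an early start. If early starting is unrelated to pain the bias disappears, and if it is commoner without pain the bias favours early gabapentin.
- *Size.* The table describes the Section 3 grouping, not a regression on time, and rests on assumed start rates.

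A further fair objection is that making a day 7 or day 14 landmark the main analysis would displace the study's own contrast, acute-hospital start or not. No document supplies those days. That stands, and the landmark is only an option below.

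**Conclusion.** The concern holds as an uncontrolled risk of confounding by indication in the gabapentin-timing DN4 model for the second primary objective. It does not extend to the time-from-injury model in the same sentence. The mechanism comes from the Introduction, and the readable plan does not list what would be needed to check or remove it. The unnamed DN4 occasion is a separate, certain gap in the model statement.

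If pain raises early starting, the Section 3 comparison is biased against early gabapentin, from slightly (1.11 for a drug with no effect) to enough to turn a true odds ratio of 0.5 into 1.52. Those figures depend on the assumed start, persistence and new-pain rates, and on borrowing the pooled 53% for this cohort. Neither size nor direction can be settled from the documents. Should-fix, with medium confidence.

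**What to change.** 1. **Section 6.** Add to the planned EMR review the date neuropathic pain was first documented. Add the reason gabapentin was started only if it will be used, for example in a sensitivity analysis that separates perioperative from pain-triggered starts.
2. **Section 7, second objective.** Name discharge DN4 as the outcome. Keep never-starters in the Section 3 comparison group. Require adjustment for neuropathic pain documented by one time point since injury that is the same for every patient. Do not use a starter's own start date for one group and a fixed day for the other.
3. **Contrast.** Keep the Section 3 grouping as a stated contrast. Pain arising after the common time point but before a later acute-hospital start is not covered by that adjustment. An optional supporting analysis reads exposure and pain at the same landmark day, set in advance by the sponsor, and includes a prevention analysis in patients free of documented neuropathic pain by that day.
4. **Fallback.** If neuropathic pain before the start cannot be abstracted reliably, report an association, not an influence of early gabapentin.

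The cost is one chart-review field, or two, and SAP wording. The downsides should be stated, with figures from the assumed day-by-day model at day 7:

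- Charting is incomplete and may differ by group. With 70% of pain documented in both groups, the no-effect prevention odds ratio is 1.02 to 1.36. With 95% in starters and 50% in others it is 0.88 to 0.97, a spurious benefit.
- The prevention analysis has few exposed patients, about 4 to 12 per 100 enrolled.
- The full-cohort landmark model adjusts away part of a real effect. If gabapentin halves the onset hazard it gives 0.59 to 0.66, against 0.48 to 0.53 in the prevention analysis.

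### DN4 status at admission and discharge is read as prevalence without regard to treatment, so a change in gabapentin uptake between the visits can be mistaken for an effect of time from injury

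*Combined protocol and SAP*

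**What the plan says.** Section 1 (Objectives) lists as its first primary objective "To determine if the time from injury influences the prevalence of neuropathic pain in acute SCI", and as a secondary objective "To determine the prevalence of neuropathic pain in those with SCI at admission and discharge to the inpatient rehabilitation hospital". The only measure of presence, in Sections 2, 6 and 10, is DN4 at two visits: one around enrollment and admission, one around discharge, each with a 7-day window. Section 7 models "dichotomous neuropathic pain (measured by DN4) as the dependent variable and time as the independent variable".

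On treatment, the Introduction states "There is evidence to support that gabapentin and pregabalin have some benefit in reducing neuropathic pain", and adds that gabapentin "is not started in all patients with acute SCI but is often started at the onset of neuropathic pain". Section 3 divides patients by whether they first received gabapentin before rehabilitation admission, and has the timing of initiation recorded. Section 6 records whether gabapentin was stopped and why; the listed reasons are lack of effect, no further need and adverse reaction.

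The reason for starting gabapentin is not on the data list in Section 6. Nor are other neuropathic pain drugs during the stay; that list has pain medication used at home before injury, and opiates. Section 7 allows confounders to enter the models on statistical or theoretical grounds but names none.

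**The concern.** DN4 at a visit describes pain present under whatever treatment the patient is then receiving. A patient who developed neuropathic pain, was started on gabapentin and now scores negative is counted with patients who never had it. By the protocol's account, treatment often follows the onset of the condition and can then remove it from the measure.

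This matters most for objective 1. Each patient's discharge visit lies later from injury than the admission visit. If the treated share of affected patients differs between the visits, part of the time coefficient reflects prescribing. A drug effect could then be reported as pain resolving with time, or a true rise could be hidden. The admission and discharge prevalences of the secondary objective have the same difficulty.

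The confounder clause does not settle it. Gabapentin use could be added as a covariate, but use is itself often triggered by the pain being modelled, so plain adjustment does not separate the two influences.

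**Working it through.** The plan states no expected change, sample size or power, so there is no figure of its own to reproduce. The check asks how large a false change could be.

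**Inputs**
- P, true prevalence: 53%, the pooled figure in the Introduction, held constant across both visits. That it represents prevalence irrespective of treatment is an assumption.
- u1 and u2, the shares of affected patients on treatment at admission and at discharge: not in the documents; assumed.
- c, the share of those treated whose DN4 turns negative: not in the documents; assumed 10% to 40%, equal at both visits.

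**Formula**

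Observed DN4 prevalence at a visit = P × (1 − u × c).

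False change, discharge minus admission = −P × c × (u2 − u1).

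**Rising uptake, u1 = 20%, u2 = 60%**

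| c | Admission | Discharge | False fall (points) | Odds ratio |
|---|---|---|---|---|
| 10% | 0.53 × 0.98 = 51.9% | 0.53 × 0.94 = 49.8% | 2.1 | 0.92 |
| 20% | 0.53 × 0.96 = 50.9% | 0.53 × 0.88 = 46.6% | 4.2 | 0.84 |
| 30% | 0.53 × 0.94 = 49.8% | 0.53 × 0.82 = 43.5% | 6.4 | 0.77 |
| 40% | 0.53 × 0.92 = 48.8% | 0.53 × 0.76 = 40.3% | 8.5 | 0.71 |

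With 80% treated at discharge, the false fall is 0.53 × 0.60 × c: 3.2 points at c = 10% and 12.7 at c = 40%.

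**Flat uptake.** With u1 = u2 the false change is zero. At 50% treated on both occasions and c = 30%, both visits show 0.53 × 0.85 = 45.1% and the odds ratio is 1.00.

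**Falling uptake.** With 60% treated at admission and 20% at discharge, the table reverses: a false rise of 2.1 to 8.5 points.

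**A true rise can be hidden.** Suppose true prevalence rises from 45% to 53% (odds ratio 1.38), uptake goes from 40% to 80% and c = 30%. Observed prevalence is 0.45 × 0.88 = 39.6% and then 0.53 × 0.76 = 40.3%, an odds ratio of 1.03.

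**Second case definition.** Counting affected patients on treatment as cases returns 53% at both visits in the constant-prevalence scenarios, whatever u and c are. This assumes that everyone counted as treated for neuropathic pain still has the condition.

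**Limit of the illustration.** These are admission-to-discharge contrasts. The model in Section 7 uses time from injury, which also varies between patients at the same visit, and the plan does not say how the two visits enter it. The bias in the time coefficient itself cannot be computed from the documents.

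**The case against.** The strongest reply is that the plan measures what it says it measures. Section 2 defines the endpoint openly as neuropathic pain present at two time points on DN4. Point prevalence under usual care is a legitimate quantity, and counting controlled pain as a case is a different one. This stands: DN4 should remain the main outcome. It does not answer how a change in that quantity is to be attributed to time from injury.

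A second reply is that rising uptake is not in the documents. Patients who received gabapentin before admission form one of the two groups, so treatment may already be common at the first visit, and stopping is recorded, so use may fall. The Introduction says often started, not always, claims only some benefit and calls treatment difficult, so conversion of DN4 may be uncommon. All of this stands, and it leaves both the direction and the size of any bias open.

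Third, start and stop data are already collected, so gabapentin status at each visit could be derived. That is correct, and it makes the repair cheap; but no analysis uses it in this way.

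A reader might also infer that the reported prevalence is too low for a population defined by its need for treatment. The documents do not support that: Sections 3 and 4 enroll any patient with acute spinal cord injury admitted to the unit who can communicate and answer questions.

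**Conclusion.** The concern holds as a conditional one. DN4 status at the two visits is a valid measure of current pain, but the plan cannot attribute a change in it to time from injury unless treatment is taken into account. The false change is P × c × (u2 − u1), with opposite sign to the change in uptake. At a constant 53% and uptake of 20% then 60%, it is a fall of about 2 points at c = 10% and about 8 points at c = 40%. Only the 53% comes from the documents.

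Two stronger readings are tempting. One is that the study will report a false fall; that needs rising uptake, which the documents do not state. The other is that DN4 is the wrong outcome, or that a change may be claimed only if both case definitions agree. The wider definition counts pain that has truly resolved on drug as a continuing case, so such a rule would work against reporting a real fall.

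Objective 2, on early gabapentin, is less affected, because fewer symptoms on the drug are partly the effect sought there. The point merits a change to the plan, with moderate confidence.

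**What to change.** 1. At each DN4 visit, derive gabapentin status from the start and stop data already recorded. Add from the EMR any other drug being given for neuropathic pain, and the charted indication.
2. Keep DN4-positive as the main outcome, label it current DN4-positive pain under usual care, and report it by treatment status at each visit.
3. Prespecify a sensitivity analysis that repeats the objective 1 model with cases defined as DN4-positive or currently treated for neuropathic pain.
4. State in advance that if the two time coefficients differ in direction, or materially in size, the change will not be attributed to time from injury alone. The team should set what counts as material before analysis; the documents give no margin.

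The cost is one EMR field per visit, one repeated model and some wording. Patient care is not altered. The drawback is that the second definition overcounts where pain has resolved on drug or the indication is poorly charted, so it serves as a check and not as a replacement.
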